5. TREATMENT OF SUBJECTS

5.1 Investigational product/treatment

Both ImCT and psychoeducation interventions are preceded by a period of 4 weeks baseline, in which they start to monitor their mood both daily and weekly, start or continue sessions with a psychiatrist (see below). Both groups will either start or continue to have regular sessions with their psychiatrist throughout the study, aimed at advice on pharmacotherapy, monitoring and if necessary adjustment of pharmacotherapy.

Description of ImCT:

The participants receive ImCT for a period of 12 weeks, 12 sessions of 60 minutes. This intervention consists of an in-depth identification (4 sessions) of images followed by imagery interventions, (6 sessions) and a consolidation phase (2 sessions) developed by Holmes, Young, Hales and DiSimplico and described in the ImCT manual (in press). The in-depth

identification consists of identifying problematic imagery, constructing a micro-formulation with the participant along the lines of regular CBT. In this micro-formulation, first triggers of problematic imagery are identified, then both quality and appraisals of this image are identified. Subsequent maladaptive behaviour and possible links with earlier experiences are described, as well as other maintaining factors. The imagery intervention consists of metacognitive imagery intervention, rescripting of imagery, promoting positive imagery or competing imagery tasks (or a combination of these). In addition, relapse prevention strategies are practiced before the end of this intervention. To increase treatment integrity, therapist in the ImCT condition receive weekly supervision from the Imagery Research group (from Oxford, London and Stockholm) via skype. Therapists are qualified psychologist carefully trained in ImCT.

Detailed description of psychoeducation:

The psycho-education lasts for a period of 6 weeks, consisting of 6 2-hour sessions. Psycho-education is offered in groups, using the format described in by Postma and colleagues (Postma, Honig, & van Gent, 2008). In the first three sessions patients are receiving information on bipolar disorder, symptoms, prevalence, aetiology and mood stabilisers. The remaining sessions focus on (early) recognition of mood variations, and management or coping strategies. Finally, medication adherence strategies and relapse strategies are discussed. Nursing staff who run the psychoeducation groups are experienced in running these groups and carefully trained in the psychoeducation method according to guidelines from Trimbos.

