4.4 Sample size calculation

To estimate the sample size needed for the between group design of this study, we used the study's primary outcome variable, mood variability, which is measured using the Affect Lability Scale (ALS-18).

The primary outcome variable for the between subjects design of the study, is the ALS-18, which was used in the audit (Hales et al., 2018) and in the pilot study by Holmes (Holmes et al., 2016). The effect sizes they found using the ALS-18 were $d = 0.8$ and $d = 0.99$ (see Table 1 below). We expect similar effect sizes in our study, that is $d = 0.9$ (the mean of the prior mentioned studies). Studies on the effect of psychoeducation have shown only moderate effects on medication adherence, knowledge of bipolar disorder and attitudes, but no or limited effect on mood variability or relapse, ranging from no effect (Bond & Anderson, 2015; Kurdal, Tanriverdi, & Savas, 2014) to a minimal effect (maximum of $d = 0.3$, but only in patients with less than 7 episodes), (Gumus, Buzlu, & Cakir, 2015; Morriss et al., 2016). We therefore expect an effect size of $d = 0.6$ (i.e., $d = 0.9$ minus $d = 0.3$). Based on prior mentioned effects of the ALS-18 we calculated the sample size needed, to power this study at 80% to detect an effect size of Cohen's $d = 0.6$ using a significance level of .05 two tailed T-tests using G*power 3.1.9.3 The calculated sample size needed is 45 in each group. The study of Holmes et al. (2016) showed a drop out 1 out of 15. After consulting with the research group from the audit and pilot study we expect a similar drop out rate in the current study. We therefore need a sample size of 48 in each group, 96 in total.

Table 1: Mean (SD) ALS-18 scores before and after ImCT in the pilot study of (Holmes et al., 2016)

Pre-Treatment	End of Treatment	4 week FU	12 week FU	24 week FU	Time	Pairwise differences, Bonferroni corrected pairwise t-test
46.36 (11.26)	35.54 (10.49)	35.43 (10.92)	36.36 (12.58)	34.71 (12.74)	F(4.48)= 6.75, $p < .001$	Pre vs 4w $t(12) = 3.77$, $p = .027$, $d = 0.99$; pre vs 12w

						$t(12)=3.58, p=.038, d = .84$; pre vs 24w $t(12)=4.62, p =.006, d = 0.97$
--	--	--	--	--	--	--

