6.2 Randomisation, blinding and treatment allocation

An independent central research assistant will randomize participants to treatment condition (ImCT or psychoeducation) after checking all in- and exclusion criteria. Randomization will be based on block randomization with (N=10) per block to guarantee a balance between conditions over time and stratified for mood stabilising medication (either mood stabilising medication, or no mood stabilising medication), so that mood stabilising medication is controlled per arm. Stratification for mood stabilising medication is necessary because not using mood stabilizing medication can seriously affect the primary outcome variable. We roughly estimate that 15 percent of the participants in GGzE will have no mood stabilising medication, but there are no firm data available. Blinding of participants and therapists to treatment condition is not possible in this kind of psychotherapy trial, but the assessments will be blind to treatment condition as they are filled in online.

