6.3.2 Study Assessment Moments

Psychoeducation groups at Centrum Bipolar start once in every six weeks. At four weeks prior to the start of each psychoeducation group the identified participants start with the online measures at baseline (T0), and both daily and weekly online measurements which participants receive by email. Note here that the patients that participate in this study will not wait longer than the patients that choose not to participate. Participants continue to fill in both the daily and weekly online measures for four weeks (the baseline period). After four weeks all participants fill in the measures pre-intervention (T1), and are allocated randomly to either the ImCT or psychoeducation condition, which will then commence. During the intervention period (12 weeks for the ImCT condition, and 6 weeks for the psychoeducation treatment condition) all participants continue to fill in both the daily and weekly online measures. At the end of the intervention, all participants fill in the post-intervention measures (T2) online. Subsequently, all participants continue to fill in both daily and weekly online measures until the end of the study (at follow up at 16 weeks). In addition, participants fill in the post-intervention online measures at follow up at 8 weeks (T3) and 16 weeks (T4) after the end of intervention.

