8. STATISTICAL ANALYSIS

First, descriptive analyses will be used to establish mean scores, standard deviations and to identify outliers. Missing data from our primary outcome variable, will be listwise deleted. In our other outcome variables, data will only be included if pre- and post-measures are completed.

Second, the data will be checked with respect to violation of assumptions (such as error independency, non-normal distributions) for variance-based models.

Primary outcome variable: mood variability:

To assess if there is a stronger decrease in mood variability in the ImCT intervention condition as compared to the psychoeducation condition, multivariate repeated measures analyses are applied. Dependent variables are the scores on the ALS-18 (baseline, T0; pre-treatment, T1; post-treatment, T2; 8-weeks follow-up, T3; 16-weeks follow-up, T4) with treatment condition (ImCT, psychoeducation) as between subjects variable.

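### Psychoeducation is given in groups, but the sample size and between-arm tests treat patients as independent; if the groups themselves make outcomes alike, standard errors are somewhat too small

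*Combined protocol and SAP*

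**What the plan says.** Randomisation is of individual patients: "An independent central research assistant will randomize participants to treatment condition" (Section 6.2). Delivery then differs by arm. For the control arm, Section 5.1 says "Psycho-education is offered in groups", in six two-hour sessions run by nursing staff, and Section 6.3.2 adds "Psychoeducation groups at Centrum Bipolar start once in every six weeks". ImCT is twelve 60-minute sessions that include "constructing a micro-formulation with the participant" (Section 5.1). That reads as individual therapy, although the protocol does not say so outright.

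The sample size is a plain two-group calculation "using a significance level of .05 two tailed T-tests", with the result "The calculated sample size needed is 45 in each group" (Section 4.4). It contains no design effect, ICC or group size. The primary ALS-18 analysis in Section 8 is a repeated-measures analysis over T0 to T4 "with treatment condition (ImCT, psychoeducation) as between subjects variable". The secondary scales use the same structure, relapse uses a chi-square test, and the post hoc comparisons are mostly independent t-tests. No therapy-group identifier or group term appears.

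The nearest safeguard is a general check in Section 8 for "violation of assumptions (such as error independency, non-normal distributions". It does not mention therapy groups and gives no action if the check fails.

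**The concern.** This is a partially nested design. Patients enter as individuals, but those in one arm are then treated together, with shared sessions, leaders and fellow patients. If that experience makes their ALS-18 outcomes resemble one another, 45 psychoeducation patients carry less information about the arm mean than 45 independent patients do. A patient-level test does not see this, so its intervals are too narrow and its p-values too small. The power figure in Section 4.4 also rests on independence.

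Although called a feasibility study, the trial states directional hypotheses (Section 2), an 80% power calculation (Section 4.4) and a Bonferroni correction (Section 8). It is also meant to inform an RCT of 350 patients. The error rate of the arm contrast therefore matters, and Bonferroni does not repair an understated standard error.

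**Working it through.** **1. The plan's own figure.** Inputs from Section 4.4: d = 0.6, two-sided 5%, t-test. With independent patients, the noncentral t distribution gives 80.4% power at 45 per arm and 79.5% at 44. The stated 45 is reproduced, so it contains no allowance for clustering.

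**2. Group size (assumption).** Six-weekly starts give 52/6 = 8.7 groups a year. If recruitment takes one year, 48 psychoeducation patients make 48/8.7 = 5.5 per group; over two years, 2.8. The recruitment period is not stated, so I use m = 3 and m = 5 trial patients per group.

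**3. ICC (assumption).** Not in the documents; I use 0 to 0.10.

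**4. Section 4.4 t-test with clustering in one arm.** Design effect DE = 1 + (m − 1) × ICC. The true standard error divided by the assumed one is √((1 + DE)/2). Example, m = 5 and ICC 0.05: DE = 1.20, ratio = √1.10 = 1.049. Power at 45 per arm, first from clustering alone (88 df), then also with Satterthwaite degrees of freedom:

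| m | ICC | SE increase | Power, clustering alone | Power, with smaller df |
|---|---|---|---|---|
| 3 or 5 | 0 | none | 80.4% | 79.4% (m = 3), 78.4% (m = 5) |
| 3 | 0.05 | 2.5% | 78.4% | 77.4% |
| 3 | 0.10 | 4.9% | 76.5% | 75.4% |
| 5 | 0.05 | 4.9% | 76.5% | 74.0% |
| 5 | 0.10 | 9.5% | 72.9% | 69.9% |

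These figures describe that single-time t-test only.

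**5. Type I error of the planned analysis.** I simulated the multivariate (Hotelling) group-by-time test on T0 to T4 with 45 per arm and 40,000 runs per cell. The group effect is absent at T0 and T1 and constant over T2 to T4. The ranges cover between-time correlations of 0.5 and 0.7, and two set-ups: group variance replacing part of the residual variance, or total between-time correlation held fixed.

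| ICC | 3 per group | 5 per group |
|---|---|---|
| 0.01 | 5.1-5.2% | 5.1-5.4% |
| 0.05 | 5.5-6.1% | 5.9-7.3% |
| 0.10 | 6.0-7.1% | 7.5-10.2% |

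At ICC 0 the test gives 4.9-5.1%, as it should.

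**6. Sensitivity to the source and duration of the correlation.** If the group effect fades (assumed weights 1, 0.5 and 0.25 at T2, T3 and T4), type I error at 5 per group and ICC 0.05 to 0.10 is about 5.7-7.4%. If the correlation is instead a calendar-cohort effect shared equally by both arms, the unadjusted test is conservative, at about 3.6-4.8% over 3 to 5 per group.

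**7. Would the independence check find it?** The chance that a one-way F test at 5% detects clustering at a single time, for ICC 0.01, 0.05 and 0.10, is 6.1%, 12.1% and 22.2% with nine groups of five, and 5.7%, 9.5% and 16.1% with fifteen groups of three. With nine groups of five and a true ICC of 0.05, the estimated ICC is zero or negative 38.7% of the time.

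**The case against.** Much of the case on the other side stands.

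- **Unknown size.** ICC, group size and recruitment period are all assumed. Section 6.3.2 suggests that groups also serve patients outside the trial, and five trial patients per group requires full recruitment in about a year. At 3 per group the inflation is small.
- **Near worst case.** The upper cells hold the group effect at full strength until 16 weeks after a six-week course. Fading lowers them (step 6).
- **Direction not assured.** Both arms begin baseline four weeks before a group starts, so ImCT patients enter in the same calendar cohorts. Correlation from season or service changes common to both arms would make the test conservative. Only correlation arising from the psychoeducation group itself does the harm described.
- **Post hoc tests.** A reader might infer that every between-arm test exceeds 5%. The documents do not support that. The post hoc tests are Bonferroni-corrected: with three comparisons and a standard error 4.9% too small, per-test error is about 2.2%, above its target of 0.05/3 = 1.7% but below 5%. The size of the effect on the relapse test and the secondary scales was not computed.
- **Limits of the remedy.** A term for psychoeducation groups leaves ImCT therapist clustering untouched. Assuming four therapists and a therapist ICC of 0.05, type I error of a test that adjusts only for psychoeducation groups was about 7.6%. The number of therapists is not in the documents.

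The planned independence check is not an adequate answer, because it names no action and would usually miss the clustering (step 7).

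**Conclusion.** The point holds in conditional form. Group delivery in one arm and the absence of any group term are plain in the text. If outcomes share a positive correlation generated by the psychoeducation groups, standard errors for the arm contrast are somewhat too small. With 3 to 5 trial patients per group and ICC 0 to 0.10, all assumed, type I error of the primary group-by-time test is about 5-7% at 3 per group and 5-10% at 5. It is lower if the effect fades by T3 to T4, and negligible near ICC 0.

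A reader might also infer that the trial is underpowered. That does not follow. The reduced power figures belong to the single-time t-test in Section 4.4, not to the repeated-measures analysis. If d = 0.6 holds throughout T2 to T4, a group-aware contrast of T2-T4 against T0-T1, with nine equal groups of five and ICC 0.10, has about 84-86% power at a between-time correlation of 0.3, and 91-92% at 0.5.

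This is a modest validity gap that is worth closing by pre-specification. It is not a fatal flaw.

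**What to change.** 1. Record each psychoeducation patient's group, including the assigned group for patients who never attend, so that the intention-to-treat set is covered.
2. Pre-specify in Section 8, for the between-arm outcomes, a partially nested mixed model: a random group effect in the psychoeducation arm after T1, with small-sample degrees of freedom. Use an analogous group-aware analysis for relapse. Keep these whatever ICC is estimated.
3. Do not substitute a Welch test on unweighted group means. Intake will probably give unequal groups, and for 45 patients in nine groups its single-time power at ICC 0 falls to about 74% with sizes from 2 to 8, and to about 67-68% with sizes from 1 to 9.
4. State in Section 4.4 that the 80% figure assumes ICC 0, and give the range from step 4 over stated ICC and group size, labelled as a property of that single-time t-test.
5. Optionally, report the estimated ICC with its interval, and add a sensitivity analysis for ImCT therapist. With about nine groups the ICC will be imprecise.

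The cost is one recorded variable and some analysis-plan text. Intervals become slightly wider. Even if the ICC is 0, the smaller degrees of freedom cost about 1 point of single-time power at 3 per group (80.4% to 79.4%) and 2 points at 5 (80.4% to 78.4%) with equal groups, and possibly more with unequal groups.

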5.2 Use of co-intervention (if applicable)

Both groups (ImCT and psychoeducation) maintain their regular consults with a psychiatrist or specialised nurse practitioner and receive advice and guidance on medication, which is monitored and adjusted conform guidelines (Goodwin et al., 2016; Kupka et al., 2015) throughout this study. These guidelines recommend using a mood stabiliser, with specific recommendation for additions in episodes of mania and depression. Where possible the above-mentioned guidelines will be adhered to unless individual circumstances warrant deviations from this. Consultation with the psychiatrist or specialised nurse practitioner will start (or continue should patients already be in care) during the baseline period, intervention period and follow-up period.

6. METHODS

6.1 Study parameters/endpoints

6.1.1 Main study parameter/endpoint

To assess the primary endpoint of this study (1), decrease of mood variability, mood variability is measured using the Affect Lability Score Short Version (ALS-18) (Oliver & Simons, 2004) at baseline (T0), pre- intervention (T1) and post intervention (T2), and at follow-up measurements at 8 (T3) and 16 weeks (T4) after treatment discontinuation in both the ImCT and psychoeducation conditions. The ALS-18 is a self-report scale measuring lability in affect and consists of 18 items. Ratings are made on a 4-point scale with a maximum score of 72. Scores range from A= very characteristic of me (4 points), to D= very uncharacteristic of me (1 point).

In addition we monitor changes in mood variability using the National Institute of Mental Health Life Chart Methodology (NIMH-LCM) Prospective Self-Rating (Denicoff et al., 2000). Participants rate their mood (both mania and depression) on a 9-point Likert scale, ranging from -4 (severe depression, admission required due to severe dysfunction) to 0 (stable mood) to +4 (severe mania, admission required due to severe dysfunction). Daily measurements are calculated during a 4-week baseline prior to start of either ImCT or psychoeducation, during the intervention and until follow up at 16 weeks. This method is advised given that traditional self-report mood ratings over a single time point are scarcely representative of mood variability in bipolar disorder.

6.1.2 Secondary study parameters/endpoints (if applicable):

The following parameters are used for the following secondary objectives:

To assess (2a) level of depression, mania and anxiety and (2b) general functioning and hopelessness (3) number of relapses into mania or depression decline/increase, we administer the following measures:

- Level of depression, using the Quick Inventory of Depressive Symptoms (QIDS-SR) (Rush et al., 2003). The QIDS-SR is a 16-item self-report rating scale in which the nine DSM 5 symptoms of major depression are incorporated. Answers are rated on a four-point Likert scale (0-3). The QIDS-SR is administered weekly throughout the duration of the study.

- Level of mania, using the Altman Self-Rating Mania Scale (ASRM-NL) (Altman, Hedekker, & Peterson, 1997). The ASRM-NL is a 5 item self-report instrument to measure severity of mania symptoms. This is administered weekly throughout the duration of the study.
- Level of anxiety, using the Beck Anxiety Inventory (BAI) (Osman, Barrios, Aukes, Osman, & Markway, 1993). The BAI is a 21-item self-report questionnaire used for measuring the severity of anxiety. Answers are rated on a 4-point Likert scale (0-3). This is administered weekly throughout the duration of the study.
- Level of general functioning and coping: Participants rate their level of functioning using the Longitudinal Interval Follow up Evaluation – Range of Impaired Functioning Tool (Leon et al., 1999). This is a brief scale for people suffering from affective disorders, measuring four different functional areas (employment, interpersonal relations, satisfaction and recreation) on a 5-point Likert scale (low rating implies higher functioning). This is administered at T0, T1, T2, T3 and T4.
- Level of hopelessness: participants rate their hopelessness using the Beck Hopelessness Scale (Beck, Brown, & Steer, 1997), The BHS is a 20 item self-report scale measuring three aspects of hopelessness: feelings about the future, motivation and expectations. The BHS demonstrates good internal consistency (alpha = .93) and has high reliability in psychiatric samples (Beck et al., 1997). The BHS is administered at T0, T1, T2, T3 and T4.
- To assess number of relapses into mania and depression, scores on the above measures (ASRM for mania and QIDS-SR for depression) are used. Scores on the ASRM of 5 or more indicate a relapse into mania, a score of 10 or more on the QIDS a relapse into depression. This is measured using the weekly scores on the ASRM and QIDS-SR during the weekly measures in the follow up period (until 16 weeks after the end of either ImCT or psychoeducation).

To assess if (4) problematic imagery the following measures will be used:

- The Visual Analogue Scales of Imagery Characteristics (VAS-Imagery) have been tailored to BD populations. The scales range from 0-9. Examples are "How real / vivid / absorbing / preoccupying / compelling have your image(s) been over the past week"; "To which extent could you understand the role that the image(s) play in your mood instability?"; "To which extent could you find positive / helpful way of using the image(s)?" Target imagery is measured weekly throughout the duration of the study. Imagery characteristics are measured weekly throughout the duration of the study in both ImCT and psychoeducation treatment conditions.

- Mental Imagery and Coping with Bipolar Disorder Questionnaire (MICQ-BD) is a 14 item self-report instrument assessing patient's response to mental imagery on a five-point Likert scale, ranging from "not at all" to "a lot". In a pilot study Holmes (2016) calculated the internal consistency ($\alpha = .70$) of this measure to be satisfactory (DiSimplicio et al., 2016). General imagery is measured at T0, T1, T2, T3 and T4.
- General Imagery (frequency of imagery, quality of imagery and appraisals of imagery) using the Dutch Imagery Survey, DImS): measured at T0, T1, T2, T3 and T4 using a 42-item online Imagery Survey recently validated in a student sample ([name], in preparation), and patient samples ([name], in preparation).

6.2 Randomisation, blinding and treatment allocation

An independent central research assistant will randomize participants to treatment condition (ImCT or psychoeducation) after checking all in- and exclusion criteria. Randomization will be based on block randomization with (N=10) per block to guarantee a balance between conditions over time and stratified for mood stabilising medication (either mood stabilising medication, or no mood stabilising medication), so that mood stabilising medication is controlled per arm. Stratification for mood stabilising medication is necessary because not using mood stabilizing medication can seriously affect the primary outcome variable. We roughly estimate that 15 percent of the participants in GGzE will have no mood stabilising medication, but there are no firm data available. Blinding of participants and therapists to treatment condition is not possible in this kind of psychotherapy trial, but the assessments will be blind to treatment condition as they are filled in online.

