4.2 Inclusion criteria

In order to be eligible to participate in this study, a subject must meet all of the following criteria:

- Aged 18-68
- Sufficient Dutch language ability to permit the assessment to be completed.
- Diagnosis of BD (I or II or unspecified) according to DSM-5 (clinicians assessment).
- Willing to complete daily and weekly monitoring throughout the duration of the study.
- Successful completion of the daily monitoring in the 4 weeks active run-in phase.
- Willing to be randomised to either ImCT or psychoeducation condition
- Able to attending 12 consecutive weekly sessions ImCT or 6 weekly two hours sessions psychoeducation/TAU.

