6.3 Study procedures

6.3.1 Screening procedures

Patients are recruited from a specialised centre for bipolar disorders in psychiatric hospital (Centrum Bipolair GGzE). The responsible lead clinician (regie behandelaar) identifies eligible patients and subsequently give these patients the information letter as well as oral information about the study and asks permission to hand over their contact information to the researcher should they consider participating. Once patients have indicated to the researcher, their nurse, psychiatrist or psychologist they would like to participate in this study, the researcher makes an appointment with the patient. During this appointment the researcher checks if the identified patient meets the inclusion criteria, and if patients still agrees with participation in the study and they are given the informed consent letter. After one week in which patients can consider their participation in this study, the researcher makes another appointment with the participant during which both the researcher and

participant sign the informed consent letter. At this time, the researcher asks for the email address of the participants in order for the online questionnaires to be accessible for the patient.

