9.2 Recruitment and consent

Patients are recruited from a specialised centre for bipolar disorders in psychiatric hospital (Centrum Bipolair GGzE). The lead clinician (regie behandelaar) identifies eligible patients and subsequently give these patients the information letter as well as oral information about the study and asks permission to hand over their contact information to the researcher should they consider participating. Once patients have indicated to their nurse, psychiatrist or psychologist they would like to participate in this study, the researcher makes an appointment with the patient. During this appointment the researcher answers any remaining questions and if patients still agree with participation in the study they are given the informed consent letter. After one week in which patients can consider their participation in this study, the researcher makes another appointment with the participant during which both the researcher and participant sign the informed consent letter. At all times can patients withdraw from the study without explanation. Moreover, they have the opportunity to consult an independent expert (dr. [name]). Note that during the whole time that patients participate in this study they are allowed to continue or start with advice on mood stabilising medication from their psychiatrist.

Once the researcher has obtained informed consent, baseline measures are administered. Patients start with four weeks daily mood measurements. At the end of these four weeks, they are randomly allocated to either ImCt or psychoeducation treatment condition and fill in the pre-intervention measurements online after which they start with either of both treatments. At the end of the treatments they fill in the post-intervention measurements online. At 8 and 16 weeks follow-up measurements the patients fill in measurements online. All patients continue their daily mood monitoring until follow-up at 16 weeks. Screening for eligibility ceases after 96 patients are included, 48 in each condition.

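### The assistant who randomises also makes the last eligibility check, beside a fixed published block of 10, a run-in criterion with no cut-off and no described concealment

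*Combined protocol and SAP*

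**What the plan says.** Section 6.2 gives randomisation and a full check of the criteria to one role: "An independent central research assistant will randomize participants to treatment condition (ImCT or psychoeducation) after checking all in- and exclusion criteria". On the method it says: "Randomization will be based on block randomization with (N=10) per block to guarantee a balance between conditions over time". There are two strata, with and without mood stabilising medication, and the smaller is a guess: "We roughly estimate that 15 percent of the participants in GGzE will have no mood stabilising medication". The section also says that neither participants nor therapists can be blinded.

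Section 4.2 lists as an inclusion criterion: "Successful completion of the daily monitoring in the 4 weeks active run-in phase". It gives no minimum number or percentage of days.

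Other roles screen earlier. In section 6.3.1, "The responsible lead clinician (regie behandelaar) identifies eligible patients", and at a later appointment, "During this appointment the researcher checks if the identified patient meets the inclusion criteria". Both steps come before consent and before the run-in. Sections 6.3.2 and 9.2 place allocation at the end of the four weeks, although they differ on whether the pre-intervention measures (T1) come before or after it. Section 6.3.2 adds that psychoeducation groups start every six weeks and that baseline begins four weeks before each group.

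On stopping, section 9.2 says: "Screening for eligibility ceases after 96 patients are included, 48 in each condition".

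The documents do not say who generates the sequence, who holds it, whether the assistant can see it, or whether eligibility is recorded before the arm is revealed.

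**The concern.** Allocation concealment means that whoever makes the final entry decision cannot know or predict the next arm. Three features here weaken the assurance of that. The last eligibility check and the draw sit with one person. One of the criteria checked at that moment is open to judgement. The block size is fixed and can be read in the protocol, at a single centre where past allocations can become known.

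If a borderline run-in patient could be accepted or refused in the light of the likely next arm, the arms could differ at entry in motivation or stability. The primary outcome, the ALS-18, is self-rated by participants who know their treatment, so sound randomisation is the main protection for the primary comparison.

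**Working it through.** **Who decides what, and when.** The lead clinician and the researcher act before the run-in, so at that stage neither can have judged run-in completion. Sections 6.3.2 and 9.2 both put allocation at the end of the four weeks. The only check described at that point is the assistant's in section 6.2. The undefined criterion therefore falls, as written, to the person who randomises.

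**Inputs.** Total 96, 48 per arm (section 4.4). Block size 10, two strata, 15% without mood stabilising medication (section 6.2), so 0.15 × 96 = 14.4 and 0.85 × 96 = 81.6 patients. Group starts every six weeks (section 6.3.2). The documents give no figure for predictability. The sample size reproduces: a two-sample t-test with d = 0.6, two-sided 0.05 and 80% power needs 44.59, so 45 per group, and 45 × 16/15 = 48. Nothing below changes it.

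**One block of 10 (five per arm), block size and past allocations known.**
- There are C(10,5) = 252 equally likely sequences. After k allocations (k ≥ 5), the next is certain if one arm is used up, with probability 2 × C(k,5)/252.
- 6th: 2 × 1/252 = 0.008. 7th: 2 × 6/252 = 0.048. 8th: 2 × 21/252 = 0.167. 9th: 2 × 56/252 = 0.444. 10th: 2 × 126/252 = 1.
- The sum is 1.67 per block, or 16.7%.
- Always guessing the arm that is behind is right 5 + (2^10/(2 × 252) − 0.5) = 6.53 times in 10, or 65.3%, against 50% by chance.

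**The whole trial, by simulation** (96 patients, strata of 15% and 85%, blocks of 10). The guesser knows every allocation, by stratum, made before the current cohort. Cohort size is not stated in the documents, so a range is shown.

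| Patients allocated together | Certain allocations of 96 | Best guess right |
|---|---|---|
| 1 | about 15 | 65% |
| 4 | about 7 | 60% |
| 6 | about 5 | 59% |
| 8 | about 4 | 57% |
| 10 | about 4 | 56% |
| 12 | about 3 | 55% |

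**Arm totals.** In about 59% of simulated trials the sequence does not end at exactly 48/48. The largest difference between arms was 6.

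**What other block sizes do.** With a fixed known size, the certain share is 33% for blocks of 4, 25% for 6, 20% for 8 and 16.7% for 10. When sizes 4, 6 and 8 are mixed at random, guessing the arm that is behind is right 67.6% of the time, against 64.6% for fixed blocks of 10. Varying the size removes most of the certainty, because the end of a block is no longer known. It does not lower the overall guess rate, and small blocks raise it.

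**The case against.** The strongest reply is that the documents never say the list is open. The assistant is described as independent and central, and a central system could hide the next arm even from that person. A reader might infer from section 6.2 that allocation is not concealed, or that entry is decided with the next arm known. The text does not support either inference; it is silent on the mechanism. This part of the reply stands.

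Most screening is done earlier by others, and checking eligibility before randomising is the normal order. That also stands, but it does not cover run-in completion. That criterion rests on online entries rather than clinical opinion, which narrows the discretion, but without a cut-off some remains.

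Allocation probably happens in cohorts tied to the six-weekly group starts, so the one-at-a-time figure is an upper case. This stands. If patients within a cohort were put in order after allocations began to be revealed, some predictability would return, but no such process is described.

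A block of 10 is fairly large and less predictable than smaller fixed blocks. That is correct, and the block size is the supporting point, not the core.

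Finally, a reader might infer from section 9.2 that the last patients are forced into the arm that is short. The sentence says when screening ends. It describes no override of the sequence, and 48 per arm can be read as the section 4.4 target. The 59% figure shows only that the two statements may not coincide.

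**Conclusion.** The point holds as a gap in the plan, not as evidence that allocation is exposed. One role makes the last check and randomises, the run-in criterion judged at that moment has no cut-off, the block size is fixed and published in a single-centre trial with open arms, and no concealment is described. Concealment therefore cannot be verified from the documents.

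The predictable part is about 15 of 96 allocations in the one-at-a-time case and roughly 4 to 5 of 96 with cohorts of 6 to 10. Both figures assume that someone tracks past allocations by stratum and that the 15% estimate is about right; the second also rests on an assumed cohort size. If the assistant could see the list itself, every allocation would be known whatever the block size, which is why the holder of the list has to be stated. The size of any resulting bias cannot be calculated from the documents. The correction is cheap and protects the primary comparison, so it should be made.

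**What to change.** 1. In section 6.2, state who generates the sequence and who holds it. Have the researcher, who does not hold the list, record and lock final eligibility in Research Manager before the assistant draws the allocation.
2. In section 4.2, define successful run-in completion by a cut-off fixed in advance, as a minimum number of the 28 days, so that the final check needs no judgement.
3. Replace the fixed block of 10 with randomly varying block sizes that are not disclosed to the centre. Avoid very small blocks, which make guessing easier.
4. In section 9.2, state that recruitment stops at 96 randomised, that 48 per arm is a target, and that the sequence is never overridden to reach it.
5. While editing, reconcile sections 6.3.2 and 9.2 on whether T1 comes before or after allocation.

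The cost is wording and a new randomisation list. Both roles already exist and the sample size does not change. Arm sizes may differ by a few patients.
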